1. Rationale for Addendum	Added 'endpoint' in place of 'objective' in brief rationale for Section 2.3.	Editorial correction
	Updated to percent change for the primary endpoint statement in brief rationale for Sections 2.3	To align with the wording used in the description of endpoints in the main protocol amendment, I4V-MC-JAHO(e)
	Revised the brief rationale statement in the table for Section 2.4.2. to state that 20 patients were enrolled into the addendum.	To align with the overall rationale.
	Updated to percent change for the primary endpoint statement in brief rationale for Section 2.9.	To align with the wording used in the description of endpoints in the main protocol amendment, I4V-MC-JAHO(e)
2.3. Objectives and Endpoints	Updated the primary objective and endpoint.	To align with the overall rationale.
	Updated Week 36 to Week 52 in third bullet for endpoints in the table.	To align with the primary endpoint of the study (Week 52).
2.4.1. Overall design	Revised the total number of patients to 20.	To align with the overall rationale.
	Removed the addendum version number 5 (2 instances) in the first paragraph.	Editorial correction.
2.4.2. Number of Participants	Revised the section to state that 20 patients were enrolled into the addendum.	To align with the overall rationale and to indicate that enrollment is completed.
2.6.1. Treatments Administered	Revised that the patients with renal impairment will not receive 4 mg QD in the footnote 'a' for Table JAHO.1. Treatment Regimen.	Updated for clarification.
2.6.7.1. Permitted Medications and Procedures	Removed the instances of Week 36 in the 4 th bullet on corticosteroid injections	To align with the primary endpoint of the study (Week 52).
2.6.7.2. Prohibited Medications and Procedures	Revised the period for temporary interruption of BCG vaccination from Week 36 to Week 52.	To align with the primary endpoint of the study (Week 52).

Section # and Name	Description of Change	Brief Rationale
2.9.1. Sample Size Determination	Revised the sample size estimation for approximately 20 patients.	To align with the overall rationale.
2.9.3.1.1. Analysis Methods	The analysis methods were revised to descriptive statistics.	To align with the descriptive nature of the study.
2.9.3.1.2. Missing Data Imputation	Added that no imputation methods will be applied and removed information on non-responder imputation and last observation carried forward.	To substantiate the use of appropriate missing data imputation techniques.

4.3.4.	Appendix 3.4. Publication Policy	61
4.4.	Appendix 4. Hepatic Monitoring Tests for Treatment-Emergent Abnormality	62
4.5.	Appendix 5. Liver Function Testing and Hepatic Safety Monitoring	63
4.6.	Appendix 6. Provisions for Changes in Study Conduct During Exceptional Circumstances	64

1. Rationale for Addendum

This addendum is a 52-week subpopulation study to better characterize the effectiveness of baricitinib therapy in Black patients with AA.

AA is a clinically heterogenous, autoimmune mediated, nonscarring hair loss disorder that varies widely in the amount and pattern of hair loss. While AA can affect people of different races and sexes, recent epidemiological studies have suggested that Black or African American patients may have a greater risk of AA (Thompson et al. 2018; Lee et al. 2020). Furthermore, Black or patients of African descent also have a higher prevalence of other comorbid alopecia, including both scarring and nonscarring forms, such as central centrifugal cicatricial alopecia and traction alopecia, which creates further diagnostic challenges in this population (Olsen et al. 2011; Raffi et al. 2019).

In the BRAVE clinical development program for severe AA, baricitinib therapy was demonstrated to be an efficacious therapy compared with placebo. While patients who were Black or African American also showed significantly greater response to baricitinib compared with placebo, the overall response rate was lower in this subgroup compared to other racial subgroups. Potential hypotheses regarding the lower response rate includes the diagnostic challenges within a large clinical trial for ascertaining primary AA in the context of other comorbid alopecia or potential subgroup differences related to hair follicle, including the rate of regrowth (Taylor et al. 2002). Therefore, this knowledge gap indicates a need to study more closely the diagnosis and treatment outcomes of Black or African American patients with severe AA. The present addendum will allow a closer examination and provide additional descriptive outcomes in response to therapy with 4-mg baricitinib in this subpopulation.

The overall changes to this addendum are provided below.

Section # and Name	Description of Change	Brief Rationale
Section 2.1. Schema for Substudy	Updated the study schema to 52 weeks	
The primary study has demonstrated the efficacy of baricitinib versus placebo at 36 weeks. As Black patients were observed to have a slower rate of response, the endpoint for this study was extended to 52 weeks.
 
Long-term efficacy and treatment withdrawal are studied in the JAHO(e) protocol and are not part of the addendum objectives.

Section # and Name	Description of Change	Brief Rationale
Section 2.2. Schedule of Activities	
 Removed visits after 52 weeks Included IWRS visit code Added Fitzpatrick scale and Hair Curl Assessment Added close-up photography views of scalp at baseline to enhance diagnostic assessment Added review of screening photographs by external expert to increase diagnostic reliability Deleted assessment related to nails 	
 Visits related to long-term extension and substudy are not needed for study objectives IWRS visits codes were added to reduce confusion with main protocol visits Fitzpatrick scale and Hair Curl assessment tools added to better characterize study population Study procedures were modified including close-up photographs to enhance diagnostic reliability with the inclusion of an independent reviewer who is an expert in severe AA in Black patients. Measure of nail assessment were removed given the lack of sensitivity to change in the JAHO study.

Section # and Name	Description of Change	Brief Rationale
	
 • Included Body Hair Symptoms and Impact, Patient Global Impression of Change, Patient Global Impression of Satisfaction • Deleted Alopecia Areata-Investigator Global Assessment, EQ-5D-5L, Short Form-36 Health Survey acute version 2, self-harm supplement, and self-harm follow-up form, and baricitinib plasma concentration (pharmacokinetic sample) • Modified footnotes as per 52-week subpopulation study 	
 • Measures for other body hair areas as well as patient satisfaction and perception of change were included to address treatment response in other body hair areas that were not included in the JAHO study. • Additional measures were deleted as these secondary objectives were identified as not relevant to the addendum. • SOA table and footnotes edited to reflect these changes.
Section 2.3. Objectives and Endpoints	
 • Modified weeks to Week 36 and Week 52 • Updated the endpoints to 	
 • The primary endpoint of this study was changed to percent change to characterize the degree of

Section # and Name	Description of Change	Brief Rationale
	
include 52 weeks
 
 Added secondary objectives related to earlier time points Deleted secondary objectives related to long-term extension and substudy Deleted secondary objectives for measures 	
improvement observed within the subpopulation of Black patients and was based on Week 52 due to the longer regrowth cycle of Black hair.
 
 Earlier time points included to describe early regrowth patterns. Removed objectives related to design elements and measures that are not relevant to addendum
Section 2.4.1. Overall Design	
 Updated as Open-label study, population to be included Black participants, and the total number of participants enrolled in the study Included 3 study periods 	As baricitinib has been demonstrated to be effective, there is no comparison to a placebo arm and outcomes are descriptive in nature
Section 2.4.2. Number of Participants	Included total number of participants to be enrolled in this study	Although the initial target of enrollment was 60 patients, 20 patients were enrolled during the enrollment period.

[figure not shown]
Section # and Name	Description of Change	Brief Rationale
Section 2.4.5. Scientific Rationale for Study Design and Section 2.4.5. Justification for Dose	Modified as per the substudy	Clarification on the objective of this addendum
Section 2.5.1. Inclusion Criteria	Included Black or African American race population	Inclusion to identify the patient subpopulation
Section 2.5.2. Exclusion Criteria	
 Included “central centrifugal cicatricial alopecia” in the criterion [8] Included “baricitinib” in criterion [10]b 	
 Clarification on potential differential diagnosis Clarification on prior exposure to JAK inhibitor
Section 2.5.3. Lifestyle Restrictions	Added additional information to clarify the use of extensions and cosmetics	Addressed the use of hair and cosmetic styling relevant to subpopulation to ensure scalp assessment
Section 2.6.1. Treatments Administered	Treatment regimen 4 mg was updated	Open-label therapy was based on 4 mg to provide the dose necessary for patients who have nearly complete or complete scalp hair loss.
Section 2.6.2. Method of Treatment Assignment and Section 2.6.8.1. Continued Access	Modified as per 52-week subpopulation study	Updated as per study design
Section 2.6.7.1. Permitted Medications and Procedures	Included nutraceuticals	Additional clarification on permitted medications
Section 2.7.2. Discontinuation from Study	Deleted that patient should remain in the study after discontinuation of IP	Not needed as study is not for regulatory submission
Section 2.8.1.2. Secondary Efficacy Assessments	
 Included as Other Clinician-reported 	
 For increased clarity

Section # and Name	Description of Change	Brief Rationale
	
Outcomes under Section 2.8.1.2.1 and Alopecia Areata Patient-Reported Outcomes under Section 2.8.1.2.2
 
 Removed eye irritation and nail assessment Added Body Hair Symptoms and Impact Scale Added Patient Global Impression of Satisfaction Added close-up photographs views with normal and polarized light 	
 Nail and eye irritation measures were not sensitive to change in the JAHO(e) protocol. Included body hair assessment tool and patient perception of change and satisfaction with treatment related to secondary objectives of the addendum Added additional photographs views to increase diagnostic reliability and detection of early regrowth
Section 2.9. Statistical considerations	
 Revised primary objective Revised secondary objectives to descriptive within subject changes 	
 Percent change of SALT score improvement was selected as primary endpoint to characterize the overall regrowth in this population. Adjusted analyses as needed for secondary objectives relevant to open-label therapy and descriptive statistics

Section # and Name	Description of Change	Brief Rationale
Throughout the document	Updated the treatment as 4-mg baricitinib Changed the word for “randomization” to “initiation” or “enrollment”	Open-label study design without randomization

2. Protocol Additions

2.1. Schema for Substudy

2.2. Schedule of Activities

	Screening Period	Treatment Period											PTFU
Visit Number	1	2	3	4	5	6	7	8	9	10	11	ET	801 ^o
Visit Code in IWRS	501	502	503	504	505	506	507	508	509	510	511		801
Weeks from Initiation		0	4	8	12	16	24	36	40	44	52		
Visit Tolerance Interval (days)	-5 to -35		±4	±4	±4	±4	±7	±7	±4	±4	±7		28±4
Inclusion and Exclusion Review	X	X											
Informed Consent	X												
Treatment Initiation		X											
Clinical Assessments													
Demographics	X												
Fitzpatrick Scale	X												
Preexisting Conditions/Medical History	X												
MPHL/FPHL History	X												
Substance Use (Alcohol, Tobacco)	X												
Previous and Current AA Treatments	X												
Chest x-ray (Posterior and Anterior View) ^a	X												
TB Test ^b	X												
Read PPD if Applicable (48 to 72 hours after V1) ^c	X												
Physical Examination	X												

	Screening Period	Treatment Period											PTFU
Visit Number	1	2	3	4	5	6	7	8	9	10	11	ET	801°
Visit Code in IWRS	501	502	503	504	505	506	507	508	509	510	511		801
Weeks from Initiation		0	4	8	12	16	24	36	40	44	52		
Visit Tolerance Interval (days)	-5 to -35		±4	±4	±4	±4	±7	±7	±4	±4	±7		28±4
12-Lead ECG (Single, Local)	X												
Height	X												
Weight	X	X	X	X	X	X	X	X	X	X	X	X	X
BMI	X	X											
Vital Signs (BP and Pulse)	X	X	X	X	X	X	X	X	X	X	X	X	X
Symptom-Directed Physical Exam ^d		X	X	X	X	X	X	X	X	X	X	X	X
MPHL/FPHL Assessment ^e								X			X	X	
Adverse Events		X	X	X	X	X	X	X	X	X	X	X	X
Concomitant Medication	X	X	X	X	X	X	X	X	X	X	X	X	X
IWRS	X	X	X	X	X	X	X	X	X	X	X	X	X
Photography Scalp ^f	X	X	X	X	X		X	X			X	X	
Photography Eyebrows/Eyelashes ^f		X	X	X	X		X	X			X	X	
Review by Sponsor Designee	X												
IP Dispensed		X	X	X	X	X	X	X	X	X			

	Screening Period	Treatment Period											PTFU
Visit Number	1	2	3	4	5	6	7	8	9	10	11	ET	801°
Visit Code in IWRS	501	502	503	504	505	506	507	508	509	510	511		801
Weeks from Initiation		0	4	8	12	16	24	36	40	44	52		
Visit Tolerance Interval (days)	-5 to -35		±4	±4	±4	±4	±7	±7	±4	±4	±7		28±4
IP Returned and Compliance Assessed			X	X	X	X	X	X	X	X	X	X	
Scales/Questionnaires													
SALT	X	X	X	X	X	X	X	X	X	X	X	X	X
Hamilton-Norwood Scale ^c	X							X			X	X	
ClinRO Measure for Eyebrow Hair Loss TM		X	X	X	X	X	X	X	X	X	X	X	X
ClinRO Measure for Eyelash Hair Loss TM		X	X	X	X	X	X	X	X	X	X	X	X
PRO for Scalp Hair Assessment TM		X	X	X	X	X	X	X	X	X	X	X	X
PRO Measure for Eyebrows TM		X	X	X	X	X	X	X	X	X	X	X	X
PRO Measure for Eyelashes TM		X	X	X	X	X	X	X	X	X	X	X	X
Body Hair Symptoms and Impact		X	X	X	X	X	X	X	X	X	X	X	
Patient Global Impression of Change				X	X		X	X			X	X	
Patient Global Impression of Satisfaction					X		X	X			X	X	
Skindex-16 for AA		X			X		X	X			X	X	X
HADS		X			X		X	X			X	X	X

	Screening Period	Treatment Period											PTFU
Visit Number	1	2	3	4	5	6	7	8	9	10	11	ET	801°
Visit Code in IWRS	501	502	503	504	505	506	507	508	509	510	511		801
Weeks from Initiation		0	4	8	12	16	24	36	40	44	52		
Visit Tolerance Interval (days)	-5 to -35		±4	±4	±4	±4	±7	±7	±4	±4	±7		28±4
C-SSRS ^g	X	X	X	X	X	X	X	X	X	X	X	X	X
Hair Curl Assessment ^h	X										X	X	
Laboratory Assessment													
Lipids (Fasting Visit) ⁱ		X			X		X	X			X	X	X
Clinical Chemistry ^j	X	X	X	X	X	X	X	X	X	X	X	X	X
Hematology	X	X	X	X	X	X	X	X	X	X	X	X	X
Serum Pregnancy Test ^k	X												
FSH ^l	X												
TSH	X												
HIV	X												
HCV antibody testing ^m	X												
HBV Testing ⁿ	X												
HBV DNA ⁿ	X				X		X	X			X	X	X
Urinalysis	X	X	X	X	X	X	X	X			X	X	X

	Screening Period	Treatment Period											PTFU
Visit Number	1	2	3	4	5	6	7	8	9	10	11	ET	801°
Visit Code in IWRS	501	502	503	504	505	506	507	508	509	510	511		801
Weeks from Initiation		0	4	8	12	16	24	36	40	44	52		
Visit Tolerance Interval (days)	-5 to -35		±4	±4	±4	±4	±7	±7	±4	±4	±7		28±4
Urine Pregnancy Test ^k		X	X	X	X	X	X	X	X	X	X	X	X
Pharmacogenetics Blood		X											
Serum Immunoglobulin (IgE)		X			X			X			X		
Exploratory Storage Samples (serum, plasma)		X			X		X	X			X	X	X
RNA and Biomarkers: Blood		X			X		X	X			X	X	X

Abbreviations: AA = alopecia areata; AGA = androgenetic alopecia; BMI = body mass index; BP = blood pressure; CKD-EPI = Chronic Kidney Disease Epidemiology Collaboration; ClinRO = clinician-reported outcome; C-SSRS = Columbia-Suicide Severity Rating Scale; ECG = electrocardiogram; eGFR = estimated glomerular filtration rate; FPHL = female pattern hair loss; FSH = follicle-stimulating hormone; HADS = Hospital Anxiety and Depression Scale; HBcAb = hepatitis B core antibody; HBsAb = hepatitis B surface antibody; HBV = hepatitis B virus; HCV = hepatitis C virus; HIV = human immunodeficiency virus; IP = investigational product; IWRS = investigator web-response system; MPHL = male pattern hair loss; PPD = purified protein derivative; PRO = patient-reported outcome; PTFU = posttreatment follow-up; SALT = Severity of Alopecia Tool; TSH = thyroid-stimulating hormone; TB = tuberculosis.

- ^a A posterior-anterior view chest x-ray will be obtained locally at Screening (Visit 1), unless one has been performed in the past 6 months and the x-ray and/or the report is available.
- ^b TB test(s) including PPD, QuantiFERON®-TB Gold, and T SPOT®. See exclusion criterion [28] for description of TB testing. In countries where the QuantiFERON-TB Gold test or T-SPOT is available, either test may be used instead of the PPD TB test. It is preferred that the QuantiFERON-TB Gold test be performed centrally; the T-SPOT must be performed locally. Note: Patients with a history of active or latent TB who have documented evidence of appropriate treatment, have no history of re-exposure since their treatment was completed, and have a screening chest x-ray with no evidence of active TB may be enrolled if other entry criteria are met. Such patients would not be required to undergo the protocol-specific TB testing, but must have a chest x-ray at screening.
- ^c If PPD testing was chosen to test for TB, then the patient must return and have the PPD test read 48 to 72 hours after Visit 1 (post-PPD).
- ^d The symptom-directed physical examination may be repeated at the investigator's discretion any time a patient presents with physical complaints.
- ^e Presence of MPHL (AGA) will be assessed at screening using the Hamilton-Norwood Scales for male patients, through examination, and via patient interview; these will be re-evaluated at Weeks 36 and 52/ET. The presence of FPHL (AGA) will be assessed at Weeks 36 and 52/ET for female patients whose history of AGA is "no history" or unknown at screening.
- ^f All sites/patients will obtain photographs of the scalp at Screening and Baseline. All sites/patients will obtain photographs of the scalp at Weeks 4, 8, 12, 24, 36, and 52, and at Early Termination. Photographs of the eyelash/eyebrows will be captured at Baseline and repeated at Weeks 4, 8, 12, 24, 36, and 52, and at early termination only from patients with AA involvement of those areas (ClinRO ≥ 1) at Baseline (Visit 2). See Section 2.8.1.4 Photography for details.
- ^g A "Baseline/Screening" form is used at Visit 1. A "Since Last Visit" form used for all remaining visits. A suicidal ideation and behavior subscales excerpt is adapted for the assessment of 11 preferred ideation and behavior categories.
- ^h Information will be collected from patients who require Spanish once the translation is available.
- ⁱ Fasting lipid profile: patients should not eat or drink anything except water for 8 hours prior to sample collection. If a patient attends these visits in a nonfasting state, this will not be considered a protocol violation. Unscheduled lipid testing can be performed at the discretion of the investigator. For ET visits, collect fasting lipids when possible.
- ^j Clinical chemistry will include the following value calculated from serum creatinine: eGFR (calculated using the CKD-EPI creatinine 2009 equation).
- ^k For all women of childbearing potential, a serum pregnancy test (central laboratory) will be performed at Visit 1. Urine pregnancy tests (local laboratory) will be performed at Visit 2 and at all subsequent study visits. If required per local regulations and/or institutional guidelines, pregnancy testing can occur at other times during the study treatment period.
- ^l For female patients ≥ 40 and < 60 years of age who have had a cessation of menses for at least 12 months, an FSH test will be performed to confirm nonchildbearing potential (FSH ≥ 40 mIU/mL).

- ^m For patients who are positive for HCV antibody, a follow-up test for HCV RNA will be performed automatically. Patients who are positive for HCV antibody and negative for HCV RNA may be enrolled.
- ⁿ Patients who are positive for HBcAb and negative for HBV DNA may be enrolled. Any enrolled patient who is HBcAb positive, regardless of HBsAb status or level, must undergo HBV DNA testing per the schedule
- ^o Visit 801 (posttreatment follow-up period) occurs approximately 28 days after the last dose of IP. Patients who have completed Week 52 and will continue on marketed product beyond Week 52 do not need to complete V801.

2.3. Objectives and Endpoints

Objectives	Endpoints
Primary Objective	
To describe the effectiveness of 4-mg baricitinib in achieving scalp hair regrowth in patients with severe AA	Percent change from baseline in SALT score at Week 52
Key Secondary Objectives (Treatment Period 2)	
To describe the effectiveness of 4-mg baricitinib in achieving regrowth as assessed by physician assessed signs and symptoms of AA	
 • Proportion of patients achieving SALT ≤ 20 from baseline through Week 52 • Proportion of patients achieving a SALT₅₀, SALT₇₅, and SALT₉₀ from baseline through Week 52 • Percent change from baseline in SALT score at Week 52 • Mean change from baseline in SALT through Week 52 • Proportion of patients achieving ClinRO Measure for EB Hair Loss 0 or 1 with ≥ 2-point improvement from Baseline through Week 52 (among patients with ClinRO Measure for EB Hair Loss ≥ 2 at Baseline) • Proportion of patients achieving ClinRO Measure for EL Hair Loss 0 or 1 with ≥ 2-point improvement from Baseline through Week 52 (among patients with ClinRO Measure for EL Hair Loss ≥ 2 at Baseline)
To describe the effectiveness of 4-mg baricitinib during open-label treatment as assessed by PRO measures	
 • Proportion of patients with PRO for Scalp Hair Assessment score of 0 or 1 with ≥ 2-point improvement from Baseline through Week 52 among patients with a score ≥ 3 at Baseline • Proportion of patients with PRO for Eyebrow Hair Loss score of 0 or 1 with ≥ 2-point improvement from baseline through Week 52 among patients with a score of ≥ 2 at Baseline • Proportion of patients with PRO for Eyelash Hair Loss score of 0 or 1 with ≥ 2-point improvement from baseline through Week 52 among patients with a score of ≥ 2 at baseline • Proportion of patients with ≥ 1-point improvement in body hair areas (nose, beard, genital) as measured by the Body Hair Symptoms and Impact scale at Week 52 • Mean change in bothersome score on each area of hair loss (nose, beard, genital) as

Objectives	Endpoints
	
measured by the Body Hair Symptoms and Impact scale at Week 52
 
 Proportion of patients who rate their AA as much improved or very much improved on the Patient Global Impression of Change scale at Week 52
To describe the effectiveness of 4-mg baricitinib during open-label treatment on emotional symptoms and quality of life	
 Mean change in HADS anxiety and depression scale scores from baseline at Week 36 and Week 52 Mean change in Skindex-16 AA emotions, functioning, and symptom scores from baseline at Week 36 and Week 52
To describe treatment satisfaction after therapy with 4-mg baricitinib for severe AA	
 Distribution of scores on the Patient Global Impression of Satisfaction at Week 52

Exploratory Objectives may include evaluating the response to baricitinib treatment on clinical measures and patient-reported outcomes. These endpoints may include dichotomous endpoints or change from baseline for the following measures: SALT, ClinROs for Eyebrows, and/or Eyelash Hair Loss™, PROs for Scalp Hair Assessment, Eyebrows, and Eyelashes™, Body Hair Symptoms and Impact, Skindex-16 AA, PGI-Change, HADS, and PGI - Satisfaction, and baseline Hair Curl Assessment.
	

Abbreviations: AA = alopecia areata; ClinRO = clinician-reported outcome; EB = eyebrow; EL = eyelash; HADS = Hospital Anxiety and Depression Scale; PGI = Patient Global Impression; PRO = patient-reported outcome; SALT = Severity of Alopecia Tool; Skindex-16 AA = Skindex-16 for Alopecia Areata.

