2.8.1.2.2. Alopecia Areata Patient-Reported Outcomes

2.8.1.2.2.1. Patient-Reported Outcomes for Scalp Hair Assessment™

Lilly has developed a novel single-item PRO assessment of the patient's current extent of scalp involvement. It is comprised of 5 category response options: 0 = no missing hair (0% of my

scalp is missing hair; I have a full head of hair); 1 = a limited area (1% to 20% of my scalp is missing hair); 2 = a moderate area (21% to 49% of my scalp is missing hair); 3 = a large area (50% to 94% of my scalp is missing hair); and 4 = Nearly all or all (95% to 100% of my scalp is missing hair) (Wyrwich et al. 2020b).

2.8.1.2.2.2. Patient-Reported Outcomes for Appearance of Eyebrows, Appearance of Eyelashes

Lilly has developed single-item PRO assessments measuring AA signs and symptoms. The PRO Measure for Eyebrows™ and PRO Measure for Eyelashes™ are single-item instruments which use a 4-point response scale, ranging from 0 = no problem to 3 = severe problem (Wyrwich et al. 2020a).

2.8.1.2.2.3. Patient-Reported Outcomes for Body Hair

The Body Hair Symptoms and Impact Questionnaire asks patients about current nasal, beard (male only), and genital hair loss. For each of these areas, patients are asked to assess the amount of hair loss using the categories of “no missing hair,” “a limited amount of hair loss,” “a large amount of hair loss,” or “complete or nearly complete hair loss.” Patients are also asked to rate how bothered they are by the hair loss using a 11-point Numeric Rating Scale of 0 to 10 where 0 is “not at all bothered” and 10 is “worst imaginable for being bothered.”

2.8.1.2.2.4. Patient-Reported Outcomes for Change

Patients will assess their overall impression of change (PGI-C) during the course of therapy. This single-item question assesses their perception of change relative to their baseline status using a 7 Likert-point scale where 1 = very much better, 2 = much better, 3 = a little better, 4 = no change, 5 = a little worse, 6 = much worse, and 7 = very much worse.

2.8.1.2.2.5. Patient-Reported Outcomes for Satisfaction

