2.9.2. Populations for Analyses

For the purpose of analyses, the following populations are defined:

Population	Description
Full Analysis Set (FAS)	All patients enrolled will be included in the FAS.
Safety Population	The safety population is defined as all enrolled patients who receive at least 1 dose of IP and who did not discontinue from the study for the reason 'Lost to Follow-up' at the first postbaseline visit.

Abbreviations: AGA = androgenetic alopecia; IP = investigational product.

- ^a Some male patients with Grade IV AGA and female patients with patterned baldness may only be identified after hair regrowth on the scalp.

Any additional analysis populations may be defined in the SAP.

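### The body-hair responder endpoint has no baseline hair-loss restriction, so unaffected patients can only count as non-improvers and the attainable rate is capped at the share affected at baseline

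*Protocol*

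**What the plan says.** Protocol addendum, Section 2.3, key secondary objectives: the proportion of patients with at least a 1-point "improvement in body hair areas (nose, beard, genital) as measured by the Body Hair Symptoms and Impact scale at Week 52". No clause says which patients are counted, or whether the three areas are reported one by one or together.

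In the same table the eyebrow PRO responder endpoint is counted "from baseline through Week 52 among patients with a score of ≥ 2 at Baseline". The eyelash PRO and the eyebrow and eyelash ClinRO endpoints use the same cut of 2, and the scalp PRO uses a cut of 3.

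A companion endpoint is the "Mean change in bothersome score on each area of hair loss (nose, beard, genital) as" measured by the same scale at Week 52.

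Section 2.8.1.2.2.3: the questionnaire "asks patients about current nasal, beard (male only), and genital hair loss". For each area "patients are asked to assess the amount of hair loss using the categories of “no missing hair" and three worse grades. The grades have no numeric scores. Bother is rated from 0 to 10.

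Section 2.9.3.1 places key secondary endpoints in the full analysis set, and Section 2.9.2 defines it: "All patients enrolled will be included in the FAS". Section 2.9.3.1.2 calls for observed-case analysis without imputation, unless the SAP adds a method. The inclusion criteria (Section 2.5.1) require at least 50% scalp loss and say nothing about nasal, beard or genital hair. The SAP does not mention the body-hair scale.

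**The concern.** A patient in the best category for an area at baseline has no room to move up. That patient still has a baseline and a Week 52 value, so an observed-case analysis keeps the patient and scores a non-response. The reported percentage then mixes how often the area was involved at baseline with how often involved areas regrew.

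The addendum's own rationale says that the body-hair measures were added to describe treatment response in areas that the parent study did not cover. The study is single-arm, descriptive and has 20 patients. No control group shares the dilution and no test is involved, so the percentage itself is the result that readers will take away.

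**Working it through.** **Which patients can respond.** The eyebrow and eyelash endpoints need an improvement of at least 2 points and are restricted to a baseline score of at least 2. That is exactly the set of patients in whom the improvement is possible. The body-hair endpoint needs at least 1 point. The matching set is patients at least one grade worse than the best category in that area, and Section 2.3 does not name it.

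**Is the gap closed elsewhere?** Eligibility does not guarantee involvement, the analysis set is all enrolled patients, and the SAP is silent on the scale. Nothing supplied closes it.

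**Inputs.** N = 20 enrolled (Section 2.4.2). The plan states no expected body-hair rate, so there is no figure of its own to reproduce. Two quantities are assumed: m, the number affected in an area at baseline, and r, the share of them who improve. All 20 are assumed to have Week 52 data. Section 2.9.4.2 specifies Wilson intervals without continuity correction but gives no numeric alpha for binary endpoints; 95% is assumed.

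**Formulas.** Restricted rate = r. Unrestricted rate = (m/N) × r. Its ceiling, reached when every affected patient improves, is m/N.

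| m of 20 | Ceiling | r | Restricted (95% CI) | Unrestricted (95% CI) |
|---|---|---|---|---|
| 5 | 25% | 60% | 3/5 = 60% (23.1–88.2) | 3/20 = 15% (5.2–36.0) |
| 10 | 50% | 60% | 6/10 = 60% (31.3–83.2) | 6/20 = 30% (14.5–51.9) |
| 15 | 75% | 60% | 9/15 = 60% (35.7–80.2) | 9/20 = 45% (25.8–65.8) |
| 20 | 100% | 60% | 12/20 = 60% (38.7–78.1) | the same |
| 10 | 50% | 40% | 4/10 = 40% (16.8–68.7) | 4/20 = 20% (8.1–41.6) |
| 15 | 75% | 40% | 6/15 = 40% (19.8–64.3) | 6/20 = 30% (14.5–51.9) |

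Rows 2 and 6 show the difficulty. An unrestricted 6/20 = 30% arises from 60% response in 10 affected patients and equally from 40% response in 15. The reported figure cannot separate the two.

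**Beard.** The item is put to men only and nothing is imputed. In a per-area analysis women have no beard value and drop out. With an assumed 8 men, all affected, and 4 improving, the plan as written gives 4/8 = 50% (21.5–78.5). The cap still applies to men who have no beard loss at baseline.

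**Bother score.** If the mean is taken over all 20 patients, with an assumed mean change of −4 in affected patients and 0 in the rest, the overall mean is −4 × m/20: −1, −2, −3 and −4 for m = 5, 10, 15 and 20.

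**The case against.** The best defence is that this is a specification detail. The endpoint is secondary and descriptive, and no test, sample size or primary result depends on it. The scale is scheduled at Week 0 and at every later treatment visit, so an affected-at-baseline denominator can be derived at any time. Sections 2.9.2 and 2.9.3.1 allow further populations to be defined in the SAP and non-principal changes to be described in the study report. If most patients have body-hair loss, the effect is small. An unrestricted summary also keeps patients who develop new loss in view. All of this stands and limits the weight of the point. None of it shows that a restriction is planned.

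A reader might go further in three ways that the documents do not support:

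- **Women dilute the beard result**, turning 4 of 8 into 4 of 20. That would require scoring women as non-improvers on an item that they are never asked, and no section provides for it. What remains is an ambiguity: if the endpoint is pooled over areas, men are judged on three areas and women on two.
- **Every other responder endpoint in the table has a baseline restriction.** The SALT endpoints and the global impression of change have none. Entry guarantees scalp loss for SALT, and the global impression is not tied to an area. The contrast holds for the scalp PRO and for the eyebrow and eyelash PRO and ClinRO endpoints.
- **The bother endpoint has the same fault.** Its wording can be read as already confined to affected areas. Unrestricted mean change is also how Section 2.3 treats HADS and Skindex-16 AA. It is ambiguous, not clearly wrong.

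**Conclusion.** The concern holds for the responder endpoint. As written, patients with no loss in an area at baseline are certain non-improvers, and the attainable rate cannot exceed the share affected. This follows from the text and needs no assumption beyond the presence of at least one such patient.

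The size is not known. The documents give neither baseline body-hair involvement nor the sex split nor an expected response. Under the assumptions above, a true 60% among affected patients is reported as anything from 15% (5 affected) to 60% (all 20 affected). It would therefore be too strong to say that the rate mainly reflects baseline involvement; that is so only if involvement is low.

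The correction is worth making because the percentage stands alone in a single-arm description. The primary endpoint, SALT percent change, is unaffected.

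**What to change.** - In Section 2.3, or in the SAP before the body-hair tables are run, define the responder endpoint separately for each area, among patients with at least the limited-loss category in that area at Visit 2. State that the beard denominator is men.
- Report the number eligible per area beside the proportion and its Wilson interval.
- List new loss in patients unaffected at baseline, since the restricted rate cannot show it.
- State that the mean change in bother uses the same affected-at-baseline patients.
- Assign numeric scores to the four hair-loss categories, so that a 1-point improvement is defined.

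The cost is a few lines of text and no new data collection. The denominator shrinks and the interval widens: with 10 affected and 6 improving, from 14.5–51.9 (37.4 points wide) to 31.3–83.2 (51.9 points wide). The wider interval shows how little 20 patients can say about regrowth in affected areas.
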